10.8 Required Routine Reporting

Adverse events to be graded at each evaluation and pretreatment symptoms/conditions to be evaluated at baseline per the CTCAE v5.0 grading unless otherwise stated in the table below:

System Organ Class (SOC)	Adverse event/Symptoms	Baseline	Each evaluation
General disorders and administrations site conditions	Fatigue	X	X
	Fever (Pyrexia)	X	X
Blood and lymphatic system disorders	Anemia	X	X
Gastrointestinal Disorders	Nausea	X	X
	Vomiting	X	X
	# of stools	X	
	Diarrhea		X

Investigations	Neutrophil count decreased	X	X
	Platelet count decreased	X	X
	AST Increased	X	X
	ALT Increased	X	X

10.81 Submit via appropriate NYU Case report forms (i.e., paper or electronic, as applicable) all AEs regardless of attribution to study treatment.

10.811 Grade 5 AEs (Deaths)

10.8131 Any death within 30 days of the patient's last study treatment or procedure regardless of attribution to the study treatment or procedure.

10.8132 Any death more than 30 days after the patient's last study treatment or procedure that is felt to be at least possibly treatment related must also be submitted as a Grade 5 AE, with a CTCAE type and attribution assigned.

11.0 Treatment Evaluation Guideline

Note: Novel combinations in AML/MDS may be expected to result in different response kinetics than "conventional" cytotoxic regimens. Thus initial blast % increase may not accurately reflect later stage responses. AraC, when given may lead to differentiation. There will be no pre-specified number of cycles and patients can remain on study as long as they tolerate the combination and/or derive clinical benefit.

11.1 AML response criteria

11.11 Complete hematologic response (CR)

Less than 5% blasts in a non-hypocellular marrow with a granulocyte count ≥ 1.0 , and a platelets count of ≥ 100 with complete resolution of extramedullary disease and absence of peripheral blood blasts.

CR incomplete (CRi) is called if patient meets all CR criteria except for residual neutropenia (ANC $< 1 \times 10^9/L$) or thrombocytopenia (platelets $< 100 \times 10^9/L$)

11.111 Complete cytogenetic remission (CCyR)

The absence of chromosome abnormalities (if present at diagnosis) on conventional cytogenetic study using G-banding (at least 10 metaphases present).

11.12 Morphologic leukemia-free state (MLFS):

If bone marrow blasts $< 5\%$, absence of Auer rods blasts, absence of extramedullary disease without hematological recovery.

11.13 Partial remission (PR)

The presence of trilineage hematopoiesis in the bone marrow with recovery of

ANC and platelet count to above levels, but with 5-25% bone marrow blasts and $\geq 50\%$ decrease in bone marrow blast percentage from baseline.

11.14 **No response (NR)**

Failure to achieve a PR, MLFS, CRi, or CR.

11.15 **Relapse:**

Disease recurrence after achieving CR. Disease recurrence is defined by blast $\geq 5\%$ in the bone marrow, or recurrence of peripheral blood blasts or extramedullary involvement.

11.2 MDS and CMML response criteria

Category	Hematologic Response Response Criteria (responses must last at least 4 weeks) ^a
Complete remission (CR)	Bone marrow: $\leq 5\%$ myeloblasts with maturation of all cell lines. If present, persistent dysplasia will be noted (dysplastic changes should consider the normal range of dysplastic changes.) Peripheral blood: 
 • Hemoglobin (Hgb) ≥ 11 g/dL (untransfused, patient not on erythropoietin) • Neutrophils $\geq 1.0 \times 10^9/L$ (not on myeloid growth factor) • Platelets $\geq 100 \times 10^9/L$ (not on a thrombopoietic agent) • Blasts 0%;
Partial remission (PR)	All CR criteria (if abnormal prior to treatment), except: Bone marrow blasts decreased by $\geq 50\%$ compared with pretreatment but still $> 5\%$. Cellularity and morphology not relevant.
Marrow CR	Bone marrow: $\leq 5\%$ myeloblasts and decrease by $\geq 50\%$ over pretreatment if $> 10\%$ at baseline Peripheral blood: if hematologic improvement (HI) responses, they will be noted in addition to the marrow CR
Stable disease (SD)	Failure to achieve at least PR, but no evidence of progression for > 8 weeks.
Failure	Death during treatment or disease progression characterized by worsening of cytopenias, increase in percentage of bone marrow blasts, or progression to an MDS FAB subtype more advanced than pretreatment after 6 months/cycles of therapy
Relapse after CR or PR	At least one of the following: 
 • Return to pretreatment bone marrow blast percentage • Decrement of $\geq 50\%$ from maximum remission/response levels in granulocytes or platelets • Reduction in hemoglobin concentration by ≥ 1.5 g/L or transfusion dependence if previously had become transfusion independent for > 8 weeks.
Cytogenetic response	Complete: Disappearance of the chromosomal abnormality without appearance of new ones Partial:

	At least 50% reduction of the chromosomal abnormality
Disease progression	
For patients with:
 
 • Less than 5% blasts: $\geq 50\%$ increase in blasts to $> 5\%$ blasts • 5%-10% blasts: $\geq 50\%$ increase in blasts to $> 10\%$ blasts • 10%-20% blasts: $\geq 50\%$ increase in blasts to $> 20\%$ blasts • 20%-30% blasts: $\geq 50\%$ increase in blasts to $> 30\%$ blasts 
Any of the following:
 
 • At least 50% decrement from maximum remission/response levels in granulocytes or platelets • Reduction in hemoglobin concentration by ≥ 2 g/dL • Transfusion dependence if previously had become transfusion independent for > 8 weeks^c
a	For a designated response (CR, PR), relevant response criteria must be noted on at least 2 successive determinations at least 1 week apart after an appropriate period following therapy (e.g., 1 month or longer).
c	In the absence of another explanation, such as acute infection, gastrointestinal bleeding, hemolysis, etc.

Hematologic Improvement*	Response Criteria (responses must last at least 8 weeks)^a
Erythroid response (pretreatment, Hgb < 11 g/dL)	Hgb increase by ≥ 1.5 g/dL Relevant reduction of units of red blood cell (RBC) transfusions by an absolute number of at least 4 RBC transfusions/8 wk compared with the pretreatment transfusion number in the previous 8 wk. Only RBC transfusions given for an Hgb of ≤ 9.0 g/dL pretreatment will count in the RBC transfusion response evaluation.
Platelet response (pretreatment, $< 100 \times 10^9/L$)	Absolute increase of $\geq 30 \times 10^9/L$ for patients starting with $> 20 \times 10^9/L$ Increase from $< 20 \times 10^9/L$ to $> 20 \times 10^9/L$ and by at least 100%
Neutrophil response (pretreatment, $< 1.0 \times 10^9/L$)	At least 100% increase and an absolute increase $> 0.5 \times 10^9/L$.
Progression or relapse after HI	At least 1 of the following: 
 • At least 50% decrement from maximum response levels in granulocytes or platelets • Reduction in Hgb by ≥ 1.5 g/dL • Transfusion dependence^b

* Pretreatment count averages of at least 2 measurements (not influenced by transfusions) ≥ 1 week apart (modification)
 
a For a designated response (CR, PR, HI), relevant response criteria must be noted on at least 2 successive determinations at least 1 week apart after an appropriate period following therapy (e.g., 1 month or longer).
 
b In the absence of another explanation, such as acute infection, gastrointestinal bleeding, hemolysis, etc.
	

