3.0 Patient Eligibility

3.1 Inclusion Criteria

- 3.11 Age \geq 18 years.

3.12 Patient population (histological or cytologically confirmed diagnosis):
Dose **escalation** part of trial for combined AraC + AZD1775 (Arm A)

- untreated elderly (>60 years) AML if in the poor-risk cytogenetic group (please reference Appendix V).

Note: previous therapy with a hypomethylating agent (HMA) for a diagnosis of MDS is allowed

Dose **expansion** part of trial for combined AraC + AZD1775 (Arm A)

- untreated elderly (>60 years) AML if in the intermediate and poor-risk cytogenetic group (please reference Appendix V)

Note: previous therapy with a hypomethylating agent (HMA) for a diagnosis of MDS is allowed

- relapsed or refractory AML (≥ 18 years)
- any MDS (≥ 18 years) having failed or been intolerant to prior hypomethylating agent (HMA) treatment.
 - Failure is defined as any disease progression while on HMA, relapse after HMA treatment or no response after 4 cycles of 5-Azacitidine or decitabine
 - Patients with isolated 5q-/5q- syndrome must have failed, not tolerated, or progressed on lenalidomide in addition to having failed or been intolerant to HMA treatment.

Note: Patients with CMML and MDS/MPN overlap are allowed if meeting other study eligibility criteria.

- advanced progressive MF, defined as intermediate and high risk primary and secondary MF, or any other MF failed or intolerant to JAK2 inhibitor therapy requiring medical therapy

Note:

- If appropriate, patients can have failed other prior therapies for their disease (i.e. JAK2 inhibitor, interferon, hydroxyurea or IMiDs). Patients may have failed more than one JAK2 inhibitor and JAK2 inhibitor must not have been the most recent treatment (e.g. other therapies as last therapy prior to study given after failure of previous JAK2 inhibitor).
- Primary (PMF) and secondary MF (post PV/post ET) are allowed.

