11.3 Response Criteria for MF

Response categories	Required criteria (for all response categories, benefit must last for ≥12 weeks in order to qualify as a response)
Complete Remission (CR)	Bone marrow: * Age-adjusted normocellularity; <5% blasts; ≤Grade 1 myelofibrosis**, AND Peripheral blood: Hemoglobin ≥100 g/L and <UNL; Neutrophil count ≥1 x 10 ⁹ /L and <UNL; Platelet count ≥100 x 10 ⁹ /L and <UNL; <2% immature myeloid cells***, AND Clinical: Resolution of disease symptoms; Spleen and liver not palpable; No evidence of EMH
Partial Remission (PR)	Peripheral blood: Hemoglobin ≥100 g/L and <UNL; Neutrophil count ≥1 x 10 ⁹ /L and <UNL; Platelet count ≥100 x 10 ⁹ /L and <UNL; <2% immature myeloid cells***, AND Clinical: Resolution of disease symptoms; Spleen and liver not palpable; No evidence of EMH OR Bone marrow: * Age-adjusted normocellularity; <5% blasts; ≤Grade 1 myelofibrosis**, AND Peripheral blood: Hemoglobin ≥85 but <100 g/L and <UNL; Neutrophil count ≥1 x 10 ⁹ /L and <UNL; Platelet count ≥50 but <100 x 10 ⁹ /L and <UNL; <2% immature myeloid cells***, AND Clinical: Resolution of disease symptoms; Spleen and liver not palpable; No evidence of EMH
Clinical improvement (CI)	The achievement of anemia, spleen or symptoms response without progressive disease or increase in severity of anemia, thrombocytopenia or neutropenia‡
Anemia response	Transfusion-independent patients: a ≥20 g/L increase in hemoglobin level† Transfusion-dependent patients: becoming transfusion-independent††
Spleen response§	A baseline splenomegaly that is palpable at 5-10 cm, below the LCM, becomes not palpable§§, OR A baseline splenomegaly that is palpable at >10 cm, below the LCM, decreases by ≥50%§§ A baseline splenomegaly that is palpable at <5 cm, below the LCM, is not eligible for spleen response Confirmation by MRI or CT showing ≥35% spleen volume reduction is recommended (but not required)
Progressive disease¥	Appearance of a new splenomegaly that is palpable at least 5 cm below the LCM, OR A ≥100% increase in palpable distance, below LCM, for baseline splenomegaly of 5 to 10 cm, OR A 50% increase in palpable distance, below LCM, for baseline splenomegaly of >10 cm, OR Leukemic transformation confirmed by a bone marrow blast count of ≥20%, OR A peripheral blood blast content of ≥20% associated with an absolute blast count of ≥1 x 10 ⁹ /L that lasts for at least two weeks

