Efficacy and safety of AZD1775 alone or with AraC will be tested in patients with relapsed/refractory AML and patients with HMA failure MDS using a flexible randomized phase II selection design. Patients will be randomized to AZD1775 alone or with AraC in a 1:1 fashion using a dynamic allocation procedure (Pocock & Simon 1975). The primary endpoint will be the complete response rate, which will be defined as an objective status of CR or CRi. Complete response rate will be evaluated over all cycles of study treatment. The proportion of CR/CRi responses will be estimated by the number of CR/CRi responses divided by the total number of evaluable patients (by arm). Two-sided 95% confidence intervals will be computed using an exact binomial confidence interval. The frequency and relative frequency of individual response categories will also be computed. Estimates will also be computed by arm separately for each disease. For a subject to be considered evaluable for statistical analysis, the subject must be eligible, provide consent, initiate treatment and not experience a major treatment violation during the first cycle of treatment.

The selected design is a flexible randomized phase II selection design (Sargent & Goldberg 2001). This study will randomize 40 evaluable patients (20 per arm). The minimum required number of CR/CRi responses for an arm to be considered as having evidence of efficacy is 3 (out of 20 evaluable patients). This decision rule is based on a single-arm single-stage binomial design testing the null hypothesis that the true CR/CRi response proportion in a given arm is at most 5% (Tawfik et al. 2014, Giles et al. 2005, Jabour et al. 2010, Prevet et al. 2011) with the smallest CR/CRi response proportion warranting subsequent studies being 25%.

In the event that both arms meet this decision rule for efficacy, the combination arm will be considered as having additional efficacy over the single-agent arm if the CR/CRi response rate on the combination arm is at least 10% greater than the single-agent arm. If the difference is <10%, then the trial is considered statistically ambiguous and the selection between the combination and single-agent arm will be allowed to include other factors (e.g., adverse event data) in addition to the CR/CRi response rate. We anticipate accruing an additional 4 patients (2 patients per arm) to account for ineligibility, cancellation, major

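### The Section 11.2 CR row requires no CR criterion to be unmet at baseline, so an MDS or CMML patient who already meets every threshold could count as a primary success by staying unchanged

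*Combined protocol and SAP*

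**What the plan says.** **Who enters.** Section 3.12 admits any MDS "having failed or been intolerant to prior hypomethylating agent (HMA) treatment" and adds that "Patients with CMML and MDS/MPN overlap are allowed if meeting other study eligibility criteria". It sets no minimum marrow blast percentage and no required cytopenia for this group. Section 5.2 places MDS, CMML and MDS/MPN overlap together in the HMA-failure group, which is randomized to Arm B or Arm C.

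**How CR is scored.** Section 11.2 is headed for MDS and CMML. Its CR row requires:
- marrow: at most 5% "myeloblasts with maturation of all cell lines. If present, persistent dysplasia will be noted";
- hemoglobin at least 11 g/dL, untransfused and off erythropoietin;
- neutrophils at least 1.0 × 10⁹/L, off growth factor;
- platelets at least 100 × 10⁹/L, off thrombopoietic agents;
- blood blasts 0%.

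The response must last at least 4 weeks. Footnote a requires two successive determinations at least a week apart, after a suitable period of therapy.

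**How CR is used.** CR plus CRi is the primary endpoint (Section 16.21). For Arms B and C, Section 16.23 states: "The minimum required number of CR/CRi responses for an arm to be considered as having evidence of efficacy is 3 (out of 20 evaluable patients"). The null rate is 5% and the stated significance level is at most 10% per arm.

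**The concern.** Every blood-count limit in the CR row is a floor. The row does not mention white cell count, monocytes, immature cells, spleen or extramedullary disease, and it asks for no change from baseline. Neither the 4-week rule nor footnote a asks for improvement; both ask only that the criteria hold over time. Someone who meets all five lines before the first dose meets them again later if nothing changes.

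In CMML this can coexist with active proliferative disease. An illustrative record is leukocytosis with an enlarged spleen, marrow blasts 4%, blood blasts 0%, neutrophils 20, hemoglobin 11.4 and platelets 160. Nothing in Section 3.12 keeps this patient out on disease grounds, and every CR line is satisfied at entry. The 11.2 progression row lists rising blasts, falling counts or hemoglobin, and transfusion dependence. A rising white count or growing spleen would therefore not end the scored response.

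An arm needs only three responses, so one that requires no treatment effect supplies a third of the evidence for activity.

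**Working it through.** **Inputs.** From Section 16.23: n = 20 evaluable per arm, at least 3 CR/CRi required, null rate 0.05, stated level at most 10%. The number k of patients in an arm who meet the whole CR row at baseline is not in the documents and is varied here.

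**1. The plan's own figures.** P(X ≥ 3), X ~ Binomial(20, p):

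| p | 0.05 | 0.10 | 0.15 | 0.20 | 0.25 |
|---|---|---|---|---|---|
| Computed | 0.0755 | 0.3231 | 0.5951 | 0.7939 | 0.9087 |
| Stated | 0.08 | 0.32 | 0.60 | 0.79 | 0.91 |

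All reproduce. The design arithmetic is sound; the issue is what counts as a response.

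**2. Upper bound with k baseline-qualifying patients.** Suppose all k stay past every threshold and the other 20 − k respond at 5%. Then P = P(Binomial(20 − k, 0.05) ≥ 3 − k).
- k = 0: 1 − (0.3585 + 0.3774 + 0.1887) = 0.0755
- k = 1: 1 − (0.3774 + 0.3774) = 0.2453
- k = 2: 1 − 0.3972 = 0.6028

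**3. One such patient who may not hold the thresholds.** Let r be the chance that this patient stays past all of them. If not, the patient is scored as not CR and the other 19 must supply three responses: 1 − (0.3774 + 0.3774 + 0.1787) = 0.0665. So P = r × 0.2453 + (1 − r) × 0.0665.

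| r (assumed) | 0.25 | 0.50 | 0.75 | 1 |
|---|---|---|---|---|
| P(≥ 3 of 20) | 0.111 | 0.156 | 0.201 | 0.245 |

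The stated 10% is passed once r exceeds (0.10 − 0.0665) / (0.2453 − 0.0665) = 0.19.

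**4. A low-frequency case.** Assume 2 of 20 have CMML or overlap, 10% of those qualify at baseline and half of these hold the thresholds. The no-effect share is 0.10 × 0.10 × 0.50 = 0.005, the effective rate is 0.05 + 0.95 × 0.005 = 0.05475, and P(≥ 3 of 20) = 0.093, inside the stated level.

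**5. Arm selection.** The 10-point margin equals two responses in 20. With both arms at a true 5%, enumerating two independent binomials gives 0.070 for selecting the combination (stated 0.07). With one patient as in step 2 in Arm B only, it is at most 0.228. MDS subcategory is a descriptive factor (Section 12.2), not a grouping factor, so balance of CMML and overlap between arms is not assured.

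**The case against.** **CR cannot be assigned on day 0.** This is correct. Footnote a and the 4-week rule both require post-treatment observation. A reader might infer that such a patient is a success at entry; the documents do not support that. They delay the classification without requiring improvement.

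**Treatment lowers counts.** This stands, and it matters. Section 1.41 lists anemia, neutropenia and thrombocytopenia as reactions to AZD1775, and Section 15.27 calls cytarabine a potent myelosuppressive agent. A patient starting at hemoglobin 11.4 has a margin of 0.4 g/dL. The 24.5% and 60.3% are therefore upper bounds, not expected error rates.

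**The frequency is unknown.** This also stands. With no such patient the error stays at 7.5%, and step 4 shows a plausible set of inputs that stays under 10%.

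**The PR row is not a missing safeguard.** A reader might take "All CR criteria (if abnormal prior to treatment), except" as a baseline condition that CR lacks. It only limits which CR criteria a PR must meet. Change from baseline enters PR through the required 50% fall in blasts.

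**Other criteria may apply.** The 11.2 heading does not name MDS/MPN overlap; its coverage is inferred from Section 5.2 and the lack of another table. Section 16.21 refers to standard criteria for the respective disease under NCCN guidelines or expert panels, but it names no set for CMML or overlap, while 11.2 expressly covers CMML.

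**Results by disease would be visible.** Section 16.23 gives estimates by arm for each disease, and Section 16.5 allows subgroup analysis by descriptive factor. That helps interpretation but does not change the 3-of-20 count.

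**Conclusion.** The point holds as a gap in the endpoint definition. The printed CR row can turn unchanged disease into a primary success in Arms B and C. Arm A enrols AML only and is unaffected.

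The size is conditional. With a 5% true rate in the other patients, the chance of declaring an arm active is 7.5% with no baseline-qualifying patient, at most 24.5% with one and at most 60.3% with two. With one such patient and an assumed 25–75% chance of holding every threshold on treatment, it is about 11–20%, above the stated level. The documents do not establish that any such patient will enrol, so they do not show that the trial's actual type I error exceeds 10%.

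Nor do they support carrying the MF requirements into CMML. Section 11.3 demands "Resolution of disease symptoms; Spleen and liver not palpable; No evidence of EMH" and caps counts at the upper normal limit, and Section 11.1 requires extramedullary disease to resolve. That contrast shows that 11.2 leaves residual proliferative disease unaddressed; it does not show which cut-offs suit CMML.

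**What to change.** **1. Baseline condition.** Add to the 11.2 CR row that a CR counts toward the primary endpoint only if at least one CR criterion was not met at baseline. State that a patient meeting all of them at baseline stays in the denominator of 20 and is scored as not CR, unless the disease-specific criteria named under item 2 are met.

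**2. Name the criteria set.** For residual leukocytosis, monocytosis, splenomegaly or extramedullary disease, the sponsor should reconcile 11.2 with 11.1, 11.3 and the general reference in 16.21. This means naming the response criteria that govern CMML and MDS/MPN overlap, rather than importing the MF cut-offs.

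**Cost.** Item 1 takes a sentence or two and uses baseline data already scheduled. A few patients counted as CR under the printed row would no longer count. Item 2 may need more data: Table 4.2 lists white cells, ANC, hemoglobin and platelets, but no monocyte or immature-cell count and no specified spleen measurement. If the named criteria use these, a differential and spleen measurement must be recorded for CMML and overlap patients.

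### The MDS/CMML relapse row in 11.2 sets a hemoglobin fall of 1.5 g/L, while every other hemoglobin threshold in that section is in g/dL

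*Combined protocol and SAP*

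**What the plan says.** Section 11.2 of the combined protocol and SAP has two tables for MDS and CMML: hematologic response and hematologic improvement.

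In the hematologic response table, relapse after CR or PR requires "At least one of the following": return to the pretreatment blast percentage, loss of half or more of the best granulocyte or platelet level, or a hemoglobin reduction of at least "1.5 g/L or transfusion dependence if previously had become transfusion independent" for more than 8 weeks. The CR row of the same table requires hemoglobin of at least 11 "g/dL (untransfused, patient not on erythropoietin"). The disease progression row includes "Reduction in hemoglobin concentration by ≥ 2 g/dL".

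In the hematologic improvement table, erythroid response is a rise of at least 1.5 g/dL, and progression or relapse after improvement includes "Reduction in Hgb by ≥ 1.5 g/dL".

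Section 16.43 runs duration of response from the first CR/CRi to the earliest documented progression. It does not mention relapse.

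**The concern.** The relapse row is the only hemoglobin threshold in 11.2 given in g/L. Taken at face value it reverses the expected ordering: a patient in complete remission would lose that status after one tenth of the hemoglobin fall needed to lose a mere hematologic improvement. No reason for such a strict criterion is given.

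The unit is not one a programmer would automatically treat as impossible, because the myelofibrosis criteria in 11.3 do use g/L. If the row is coded as printed, ordinary variation in blood counts could produce relapse labels for MDS/CMML responders. Whether those labels reach a reported endpoint depends on how 16.43 is read, and duration of response is a listed secondary goal (2.23).

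**Working it through.** **Inputs from 11.2.** Relapse after CR or PR: fall of 1.5 g/L. Relapse after hematologic improvement: fall of 1.5 g/dL. Disease progression: fall of 2 g/dL. CR floor: 11 g/dL.

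**Unit conversion.** 1 g/dL = 10 g/L, so 1.5 g/L = 1.5 / 10 = 0.15 g/dL.

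| Row in 11.2 | Fall, g/dL | Ratio to 0.15 | Share of 11 g/dL |
|---|---|---|---|
| Relapse after CR or PR, as printed | 0.15 | 1 | 0.15/11 = 1.4% |
| Relapse after hematologic improvement | 1.5 | 1.5/0.15 = 10 | 1.5/11 = 13.6% |
| Disease progression | 2 | 2/0.15 = 13.3 | 2/11 = 18.2% |

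The tenfold comparison is with the hematologic improvement table. Within the hematologic response table itself, the only other hemoglobin-fall threshold is the 2 g/dL for progression, so the gap there is 13.3-fold.

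**Is one reading enough?** As written, yes. The footnote requiring two successive determinations is worded for designated responses, not for relapse. The footnote excusing other explanations, such as bleeding or infection, is attached in the progression row and not here.

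**How often would chance alone trigger it?** The documents give no hemoglobin SD, so this is an illustration. Assume true hemoglobin is stable, readings vary independently and normally with SD s, and the fall is measured from one reference reading. For one later reading, P(fall ≥ t) = 1 − Φ(t / (s√2)). For example, with t = 0.15 and s = 0.1, 0.15 / 0.1414 = 1.06 and P = 14%. The six-reading figures come from simulating 200,000 patients.

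| Assumed s, g/dL | One later reading, 0.15 | Any of six, 0.15 | One later reading, 1.5 | Any of six, 1.5 |
|---|---|---|---|---|
| 0.1 | 14% | 42% | 0% | 0% |
| 0.2 | 30% | 66% | 0% | 0% |
| 0.3 | 36% | 74% | 0.02% | 0.1% |
| 0.5 | 42% | 79% | 1.7% | 7.3% |

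**Does it reach the duration endpoint?** Section 16.43 stops the clock at documented progression, and the MDS progression row uses 2 g/dL. On that reading the 1.5 g/L row is never used. However, the AML criteria in 11.1 define relapse and no category of progression. Arms B and C mix AML and MDS, so 16.43 has a defined AML disease event only if relapse is counted as progression. Carrying that reading over to MDS brings in the 1.5 g/L row. The plan does not say which reading applies.

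**The case against.** The strongest reply is that this is an obvious slip with little reach. A change of 1.5 g/L fits neither the g/dL values in 11.2 nor the g/L values in 11.3 (85, 100 and a change of 20), so a careful reader would notice it. The row is not named in 16.43. Treatment continuation (13.1 and 13.2) turns on progressive disease, not on this row. AML relapse (11.15) and MF relapse (11.3) do not use the threshold. Duration of response is estimated only in CR/CRi responders: with 20 evaluable patients per arm and design rates of 5% to 25%, that is 20 × 0.05 = 1 to 20 × 0.25 = 5 expected per arm, of whom only the MDS/CMML patients use 11.2. The estimate is a Kaplan-Meier curve with no decision rule.

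All of this stands as a limit on the consequence. It does not remove the inconsistency, and being easy to recognise lowers the risk of literal coding without ruling it out.

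A reader might also infer that almost every responder would relapse at the next blood count. The figures do not support that: under the assumptions above, the one-reading probability is 14% to 42% and stays below 50% at any SD. Nor do the documents support saying that duration of response is destroyed, because that requires counting relapse as progression.

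**Conclusion.** The unit in the relapse row is wrong as written: 0.15 g/dL against 1.5 and 2 g/dL for the comparable falls in 11.2, a factor of 10 and 13.3. This rests on the documents alone. The false-relapse percentages rest on an assumed SD of 0.1 to 0.5 g/dL, independent normal readings and a single reference reading, and should be cited only as an illustration.

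The reach is limited to MDS/CMML responders in Arms B and C. Duration of response is exposed only through the open question in 16.43.

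A reader might infer that the primary endpoint is at risk too, since 11.2 says "responses must last at least 4 weeks" and an early relapse label could seem to cancel a CR. The documents do not support this. The four-week and two-determination rules ask whether the response criteria themselves continue to be met: a patient who falls from 11.5 to 11.3 g/dL (a drop of 0.2) passes the printed relapse threshold yet still meets the 11 g/dL hemoglobin floor. The CR/CRi rate is evaluated over all cycles, and later relapse does not undo it. Sample size, power and decision rules do not depend on this row.

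**What to change.** 1. In 11.2, row Relapse after CR or PR, change the hemoglobin unit from g/L to g/dL so that it agrees with the rest of the section. This is a one-unit correction.

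2. In 16.43, state whether relapse ends a response. If it does, reconcile the two hemoglobin triggers that would then apply to MDS/CMML (1.5 g/dL for relapse once corrected, 2 g/dL for progression) and say which one stops the clock. This is more than a typographical change, because it settles the event definition of a secondary endpoint, but it needs only a sentence or two and no change to sample size.

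Both should be done before responses are coded. Adding relapse to 16.43 without correcting the unit would write the misprint into the endpoint.
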